6.4 Analysis of Efficacy

No efficacy analyses will be conducted in this OLE SAP.

6.5 Analysis of Safety

Analysis population: SAF, Analysis group: ASP0367 any dose group or Placebo to ASP0367 group

6.5.1 Adverse Events

AEs will be coded using the MedDRA.

An overview table will include the following:

- Number of TEAEs,
- Number and percentage of participants with TEAEs,
- Number of drug related TEAEs,
- Number and percentage of participants with drug related TEAEs,
- Number of serious TEAEs,
- Number and percentage of participants with serious TEAEs,
- Number of serious drug related TEAEs,
- Number and percentage of participants with serious drug related TEAEs,
- Number of TEAEs leading to death,
- Number and percentage of participants with TEAEs leading to death,
- Number of drug related TEAEs leading to death,
- Number and percentage of participants with drug related TEAEs leading to death,
- Number of TEAEs leading to withdrawal of study drug,
- Number and percentage of participants with TEAEs leading to withdrawal of study drug,
- Number of drug related TEAEs leading to withdrawal of study drug,
- Number and percentage of participants with drug related TEAEs leading to withdrawal of study drug, and

• Number of deaths.

The number and percentage of participants with TEAEs, as classified by SOC, and PT will be summarized by analysis group. Summaries will be provided for the following:

- TEAEs.
- drug related TEAEs,
- serious TEAEs,
- drug related serious TEAEs,
- TEAEs leading to withdrawal of study drug,
- drug related TEAEs leading to withdrawal of study drug,
- TEAEs excluding Serious AEs that equal to or exceed a threshold of 5.0% in any analysis group.

The number of TEAEs and the number and percentage of participants with TEAEs, as classified by SOC and PT will be summarized by severity and by relationship to study drug. In the participant count, if a participant has multiple TEAEs with the same SOC or PT, but with differing severity or relationship, then the participant will be counted once with the worst severity and highest degree of relationship. If severity or relationship is missing for all episodes of the event, the participant will be counted under missing severity or relationship.

The following AESIs are defined:

- Cardiac tissue injury defined by cTnI above ULN or if the cTnT is above ULN or baseline if the participant's baseline value was above ULN and a TEAE as pre-defined by a MedDRA search strategy for elevated troponin.
- Cardiac tissue injury with any signs or symptoms defined by an echocardiogram or electrocardiogram interpretation is reported as abnormal, clinically significant and a TEAE as pre-defined by a MedDRA search strategy for cardiac complaints.
- Skeletal muscle injury defined by CK increase >= 5 times the value of the ULN or the individual's baseline value, whichever is higher and a TEAE as pre-defined by a MedDRA search strategy for skeletal muscle injury.

AESIs prior to version 9.0 of the protocol did not include elevations in cTnT in the definition of an AESI but instead only included elevations of cTnI. All participants participated in protocol version 7.0 or earlier; therefore participants for whom elevations in cTnT were observed may not have been identified as having experienced an AESIs during study conduct and for this reason may not have had additional ECG and echocardiographic evaluations performed.

The number and percentage of participants who report AESIs will be summarized by analysis group. In addition, any (serious) AEs that are considered abuse of the study drug will also be collected and followed. The number and percentage of AEs of special interest related to abuse, as classified by SOC and PT will be summarized by analysis group.

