1 INTRODUCTION

This SAP contains technical and detailed elaboration of the principal features of the analysis described in the protocol and includes procedures for executing the statistical analysis to fulfil the objectives of the study.

The study was designed to be, and executed as, a double-blinded with an OLE. The OLE was removed from protocol version 9.0 and so the use of the present tense is no longer accurate. In addition to the objectives and endpoints defined in Study 0367-CL-1201 protocol (core protocol), some additional objectives and endpoints specific to the Mayo Clinic (Minnesota) had been defined in Study 0367-CL-1201 [MAYO] Protocol. However, as there have been no participants recruited to the protocol from the Mayo sites, therefore there will be no SAP created. Until protocol version 7.0, the double-blinded period was 52 weeks and open label extension period was 24 weeks. However, from protocol version 8.0 onwards, the doubleblinded period was revised to 24 weeks and in protocol version 9.0 the OLE period was removed. Since no participants have been evaluated under protocol version 8.0 or later, two SAPs will be prepared: one for analyses up to 52 weeks of treatment (the double-blind part of the study), and the other one for analyses at the end of 76 weeks of treatment (the doubleblind part and the OLE part of the study). In this analysis, participants assigned ASP0367 in the double-blinded period will be analyzed for through the double-blinded part and the OLE part of the study including follow-up visit, while participants switched from Placebo to ASP0367 in the OLE part will be analyzed in the OLE part only including follow-up visit. This document is an analysis plan for the up to 76 weeks (double-blinded part and OLE part of the study) including follow-up visit.

Analyses for pharmacokinetic and pharmacodynamic (target gene expression and biochemical markers) endpoints, including exposure-response assessment, will be described in the separate analysis plan and this SAP only focus on safety endpoints.

This document will be finalized prior to the database lock at the end of study. If there are any changes from the planned analyses in the final version of the SAP that impact the statistical analyses, then it will be documented in the CSR.

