6 STATISTICAL METHODOLOGY

6.1 General Considerations

Continuous data will be summarized descriptively including the number of participants (n), mean, standard deviation (SD), median, minimum and maximum. Categorical data will be summarized by frequencies and percentages. Percentages by categories will be based on the number of participants with no missing data, i.e. the percentages for the non-missing categories will add up to 100%.

There are 2 different groups defined based in the randomization group:

- ASP0367 any dose group: Participants randomly assigned to ASP0367.
- Placebo to ASP0367 group: Participants randomly assigned to placebo and who continue into the OLE and receive ASP0367.

Safety analysis and other summaries based on SAF will be presented by analysis group (ASP0367 any dose group or Placebo to ASP0367 group), unless specifically stated otherwise.

All data summarization and analyses will be performed using SAS® Version 9.4 or higher on Linux. Specifications for table, figures, and data listing formats can be found in the TLF specifications.

For continuous variables that are recorded as "<X", "<=X", ">X", or ">=X", the value of "X" will be used in the calculation of summary statistics if otherwise noted. This approach may result in a summary that reflects the presence of an analyte (such as troponin) when in fact the analyte was not detected but reported as less than the lower limit of detection by the assay.

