6.2.3 Demographic and Other Baseline Characteristics

Analysis population: SAF, Analysis group: ASP0367 any dose group, Placebo to ASP0367 group and Total

• Demographic and other baseline characteristics (age, sex, race and ethnicity, body weight, height and BMI) will be summarized by descriptive statistics and frequency tabulations [Table 1].

Table 1 Demographic and baseline characteristics

Item	Classification
Sex	1: Male
	2: Female
Age (Years) [Informed Consent]	Measurement value
Age	1: >=18 to <65
8	2: >=65 to <=80
Ethnicity	1: Not Hispanic or Latino
	2: Hispanic or Latino
Race	1: White
	2: Black or African American
	3: Asian
	4: American Indian or Alaska Native
	5: Native Hawaiian or Other Pacific Islander
	6: Other
Height (cm) [Screening]	Measurement value
Weight (kg) [Screening]	Measurement value
BMI (kg/m^2) [Screening]	Measurement value
BMI	1: < 25
	2: >=25
Site Group	1: Mayo clinic Minnesota
•	2: Non-Mayo clinic Minnesota
Walking aid use [Baseline [†]]	0: No
	1: Yes
Duration of disease (Years) [‡]	Measurement value
Treated with medication [Screening]	0: No
	1: Yes
Syndrome	1: Kearns Sayre Syndrome (KSS)
	2: Mitochondrial Encephalomyopathy, Lactic Acidosis and
	Stroke-like episodes (MELAS)
	3: Maternally Inherited Diabetes Deafness (MIDD)
	4: Myoclonic Epilepsy with Ragged Red Fibers (MERRF)
	5: Chronic Progressive Externa Ophthalmoplegia (CPEO)
	6: 3-methylglutaconic aciduria, Deafness, Encephalopathy,
	and Leigh-like disease (MEGDEL)
	7: Leigh Syndrome
	8: Multisystem mitochondrial disorder
	9: Mitochondrial Myopathy
	10: POLG-related disorders
	11: Others
Genetic abnormality	1: Mitochondrial DNA
NO. 1 11 IDAY	2: Nuclear DNA
Mitochondrial DNA mutant heteroplasmy	0: No
information is available	1: Yes
Level of heteroplasmy (%)	Measurement value

BMI: body mass index; CPEO: Chronic Progressive Externa Ophthalmoplegia; KSS: Kearns Sayre Syndrome;

MEGDEL: 3-methylglutaconic aciduria, Deafness, Encephalopathy, and Leigh-like disease; MELAS: Mitochondrial Encephalomyopathy, Lactic Acidosis and Stroke-like episodes; MERRF: Myoclonic Epilepsy with Ragged Red Fibers; MIDD: Maternally Inherited Diabetes Deafness; POLG: polymerase-gamma.

†: For participants received ASP0367 on double blind part, the measurement at week 0 will be used as baseline, and for participants received placebo on double blind part, the measurement at week 52 will be used as baseline.

‡: Duration of disease will be calculated as follows:

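### The 76-week SAP shows crude safety percentages side by side for groups with up to 80 and up to 28 weeks at risk, with no allowance for time at risk

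*SAP*

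**What the plan says.** The SAP document contains two plans, one for the double-blind part and one for up to 76 weeks. This point concerns the second, called here the 76-week SAP.

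- **Period lengths (section 1).** "Until protocol version 7.0, the double-blinded period was 52 weeks and open label extension period was 24 weeks". The older design governs the data: "Since no participants have been evaluated under protocol version 8.0 or later".
- **Who is counted when (section 1).** "participants assigned ASP0367 in the double-blinded period will be analyzed for through the double-blinded part and the OLE part", whereas "participants switched from Placebo to ASP0367 in the OLE part will be analyzed in the OLE part only including follow-up visit".
- **Columns (6.1).** One is ASP0367 any dose. The other is Placebo to ASP0367, defined as "Participants randomly assigned to placebo and who continue into the OLE and receive ASP0367".
- **Switch point (6.2.3, footnote on walking-aid use).** "for participants received placebo on double blind part, the measurement at week 52 will be used as baseline".
- **TEAE window (5.2.1).** From the first ASP0367 dose to 28 days after the last.
- **Summary measure (6.5.1).** "Number and percentage of participants with TEAEs". The same form is used for serious TEAEs, withdrawals and AESIs. Sections 6.5.2 and 6.5.2.1 use it for amylase, lipase, troponin and liver thresholds over the same window. One table lists non-serious TEAEs that reach 5.0% in any group.
- **Exposure (6.3).** Duration on ASP0367 is tabulated in bands up to day 533 but is never used as a denominator for events.

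**The concern.** A crude percentage is the chance of at least one event during the time a person is watched, so it rises with that time even when the underlying risk is the same. Here one column may be watched almost three times as long as the other, and no rate, time-to-event estimate or equal-window table lets the reader separate risk from duration.

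Safety is the only subject of this SAP (sections 1 and 6.4). Protocol 2.3.1.3 names cardiac and skeletal muscle toxicity as important potential risks, and such uncommon events are where unequal windows distort most. The any-dose column could look more toxic only because it was followed longer, or a higher early rate in switchers could be hidden.

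**Working it through.** **The plan's own figure.** 52 + 24 = 76 weeks; 76 × 7 + 1 = day 533, which matches the top exposure band in 6.3. Week 52 is day 365, and (533 − 365)/7 = 24 weeks of OLE. Section 2.2 refers to a 52-week OLE, but the period lengths in section 1 and the week-52 baseline for switchers both point to 24 weeks for this cohort.

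**Maximum windows.** Any dose: 76 + 4 = 80 weeks. Switchers: 24 + 4 = 28 weeks. Ratio 80/28 = 2.86.

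**Equal risk, unequal windows.** The documents give no event rate, so I assume a constant rate r of first events per participant-year, the same in both columns, with everyone reaching the maximum. Then P = 1 − exp(−r × weeks/52).

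| r per year | Any dose, 80 weeks | Switchers, 28 weeks | Ratio |
|---|---|---|---|
| 0.1 | 14.3% | 5.2% | 2.7 |
| 0.2 | 26.5% | 10.2% | 2.6 |
| 0.5 | 53.7% | 23.6% | 2.3 |
| 1 | 78.5% | 41.6% | 1.9 |
| 5 | 100% | 93.2% | 1.1 |

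**The 5.0% listing rule.** An event with 2% risk in 28 weeks has 1 − 0.98^(80/28) = 5.6% risk in 80 weeks, so duration alone carries it over the threshold.

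**Sensitivity to the assumptions.**
- *Dropout.* Simulating 10% loss per 24 weeks (an assumption; mean exposure about 65 and 23 weeks) leaves ratios of 2.4, 2.4 and 2.1 at r = 0.1, 0.2 and 0.5.
- *Shorter actual exposure, r = 0.2, 28 days added.* At 52 against 24 weeks: 19.4% and 10.2%, ratio 1.9. At 52 against 12: 19.4% and 6.0%, ratio 3.25. At 28 against 24: 11.6% and 10.2%, ratio 1.1.
- *Front-loaded risk.* Take 20% by 28 weeks and a Weibull hazard with shape k, so that P at 80 weeks = 1 − exp(ln 0.8 × (80/28)^k). This gives 47% at k = 1 (constant), 31% at k = 0.5 and 25% at k = 0.25.

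**Comparison with placebo.** The double-blind SAP counts placebo TEAEs to 28 days after the last double-blind dose or the move to the OLE, whichever is first (5.4.1), and its liver window is tied to 52 weeks (6.5.2.1). The maximum is therefore about 52 + 4 = 56 weeks. At r = 0.5, 1 − exp(−0.5 × 56/52) = 42%, against 54% at 80 weeks.

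**Does a remedy work?** In the dropout simulation at r = 0.2, the crude percentages are 22.9% and 9.7%. Rates per 100 participant-years are 20.0 and 19.9. Cutting both columns at 28 weeks from the first ASP0367 dose gives 9.7% and 9.7%. Under a constant hazard, either remedy removes the artefact.

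**The case against.** The 76-week SAP plans no test or contrast between its columns. The concurrent comparison with placebo is in the double-blind SAP, which shows 30 mg, 75 mg, any dose and placebo. The column label announces the switch and exposure is tabulated for the same two groups, so a careful reader can see the imbalance. This stands, and it limits the harm to misreading. It does not supply a comparable figure, because an exposure table cannot be converted into an event rate by eye.

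Three stronger readings are tempting, and the documents support none of them.

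- *That every row will look very different.* The table above needs full exposure and a constant hazard. Near-universal rows and strongly front-loaded events move little.
- *That the early stop made exposure still more uneven.* The monitoring committee recommended stopping for futility (6.7.1), but no exposure data after that are given. Stopping could have shortened either column, and the scenarios above run from 1.1 to 3.25.
- *That the placebo percentages cover 24 weeks.* Protocol 9.4.3.1 sets a day-182 limit for participants who stayed on version 7.0 or earlier, but the double-blind SAP does not carry it over. Only its efficacy inference is at week 24.

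The remedy also has limits. Events per participant-year presume a roughly constant hazard. Neither a rate nor an equal window corrects for selection: switchers had to stay through the double-blind part, whereas ASP0367 participants who left early remain in the safety set (4.1).

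**Conclusion.** The point holds as a matter of presentation. The two columns have maximum windows of 80 and 28 weeks, and the planned event, laboratory and liver tables make no allowance for it. At equal constant risk and maximum exposure, the any-dose percentage is about 2 to 3 times the switcher percentage for rates of 0.1 to 1 per participant-year. That is an illustration: it rests on assumed rates, a constant hazard and full exposure, and the true ratio could be close to 1. The any-dose column also does not share a window with the double-blind placebo column, though that mismatch is milder. No inference in the plan is invalidated. This is a cheap improvement to the one topic the 76-week SAP covers.

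**What to change.** 1. **Reconcile the last-dose date first.** The 76-week SAP 6.3 builds it from the Phase 2, dose-selection and OLE dates. The double-blind SAP 6.3 also includes the Phase 3 Treatment Period date. Without that date, participant-time could be wrong for anyone who stopped in that period.
2. **Add an equal-window display.** For TEAEs, serious TEAEs, AESIs and the laboratory and liver threshold tables, show both columns restricted to the first 24 weeks on ASP0367, with the same 28-day follow-up rule.
3. **Add exposure-adjusted incidence.** For TEAEs, serious TEAEs and AESIs, give participants with an event per 100 participant-years to first event or censoring, with confidence intervals.

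Keep the crude tables. The cost is a few extra tables and no new data. Intervals in the small switcher group will be wide. A table note should say that the rates presume a roughly constant hazard and that switchers are a selected group. Section 1 already provides for documenting changes to the planned analyses in the CSR.

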6.5.2 Clinical Laboratory Evaluation

Quantitative values including hematology, biochemistry, and urinalysis will be summarized using mean, standard deviation, minimum, maximum and median by analysis group at each analysis visit. Additionally, a within-participant change will be calculated as the post-baseline measurement minus the baseline measurement and summarized in the same way. Each laboratory result will be classified as low (L), normal (N), or high (H) at each visit according to the site supplied reference ranges. For the Placebo and ASP0367 groups, baseline values for CK-MM and CK-MB will be defined as the last non-missing observation prior to the first administration of ASP0367.

Frequency tabulations of qualitative clinical laboratory variables (urinalysis) will be presented for each analysis group at each visit.

Additionally, amylase, lipase and troponin elevations above the ULN and 2xULN will be summarized by analysis group. The denominator for each criterion will be the number of participants who have at least one value after the day of first ASP0367 taken to 28 days after the last dose of ASP0367. The number and percentage of participants meeting the criteria by 28 days after the last dose of ASP0367 will be summarized by analysis group.

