- g. Safety laboratory will be done by a central laboratory from the screening to EOS. Blood collection for hematology and biochemistry; muscle biomarkers include CK, CK MM, CK-MB and cardiac troponins I and T. Urinary creatinine should be analyzed quantitatively like blood creatinine analysis that will be used for correcting urinary TITIN. Biochemistry and hematology samples will be taken prior to study assessment, except for ECG and vital signs. At follow-up phone call visits, abbreviated biochemistry (including cardiac troponin I) will be collected at the participant's home (abbreviated hematology will only be collected at week 2) by a qualified healthcare provider from the home healthcare vendor. In case the home healthcare visit is not feasible, the visit can be conducted at the study site.
- h. Serum pregnancy tests will be performed for WOCBP.
- i. Urine pregnancy tests will be performed for WOCBP.
- j. ECGs should be performed prior to blood draw. ECGs will be recorded in triplicate (3 separate ECGs with 5-minute resting prior to first ECG and at least 1 minute apart per time point). In addition, ad hoc triplicate ECG may be required to follow up on an elevation of cTnI above the ULN (see Appendix 10.9 for reference range), or when there is an elevation of cTnT above the ULN (see Appendix 10.9 for reference range) or above the participant's baseline value if it was elevated, or when a participant has any signs or symptoms reflecting cardiac involvement, inclusive of new onset shortness of breath. If the QTcF > 450 msec in male participants and > 480 msec in female participants at screening or randomization, one additional triplicate ECG can be performed on the same day in order to determine the participant's eligibility. ECGs at weeks 2 and 8 will be performed at the participant's home by a qualified healthcare provider from the home healthcare vendor. In case the home healthcare visit is not feasible, the visit can be conducted at the study site.
- k. At screening, the "Screening" version is to be used to determine eligibility. During all subsequent visits, the "Since Last Visit" version is used to monitor on-study suicidal ideation and behavior after the initial assessment.
- 1. Following randomization, participants will be encouraged to perform all 6MWTs within a 2-hour window of the performance time recorded during visit 2.

Footnotes continued on next page

- CONFIDENTIAL -

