2.3.1.2 Clinical

ASP0367 has been assessed in 4 completed phase 1 clinical studies (0367-CL-0001, 0367-CL-1102, 0367-CL-1103 and 0367-CL-1111). ASP0367 was well tolerated in the healthy adult participants and participants with mild or moderate hepatic and severe renal impairment. There were no deaths and no serious adverse events (SAEs) reported. Also, there were no discontinuations due to treatment-emergent adverse events (TEAEs). All adverse events (AEs) were transient and mild or moderate in severity. No drug-related cardiac or skeletal muscle AEs were reported. In the first-in-human Study 0367-CL-0001, one participant at the single dose of 60 mg had cTnI values above the upper limit of normal (ULN; 0.056 ng/ml and 0.047 ng/mL above the ULN of 0.045 ng/mL) at the end of study visit (8 days after a single dose) and repeat assessment poststudy on day 21, respectively, with no clinical signs associated and deemed not clinically relevant. There was no test article-related elevation in serum cTnT; CK-MB stayed within the normal range, and no participants were observed with ischemic changes or prolonged QT. Amylase and lipase elevations above the laboratory reference range were observed for a number of participants following administration of ASP0367 or placebo. There were no trends for treatment or dose, or day of onset-related trends in the frequency or magnitude of these elevations. The participants with amylase or lipase elevations remained asymptomatic and the elevations resolved without treatment. None of the amylase or lipase elevations were reported as TEAEs. There were no other clinically significant findings in laboratory tests (specifically in skeletal and other cardiac muscle markers [cTnT, CK-MB]), vital signs or electrocardiograms (ECGs; changes related to ischemia or QT interval changes).

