In Studies 0367-CL-1102 (mild and moderate hepatic impaired participants and healthy matched participants) and 0367-CL-1111 (severe renal impaired participants and healthy matched participants), the incidence of TEAEs reported during study conduct was low. In each study, 2 TEAEs were reported that were considered by the investigator to be mild and related to study intervention. In the hepatic impairment study, 1 participant with mild hepatic impairment experienced nausea and 1 participant with mild hepatic impairment experienced fatigue. In the renal impairment study, 1 participant with severe renal impairment had a TEAE of troponin I increased (single episode with onset on day 2; value of 0.09 ng/mL [normal range: not reported to 0.015 ng/mL]) and 1 participant with severe renal impairment had a TEAE of lipase increased (values above ULN of 92 U/L on day 5, 142 U/L at EOS visit and 85 U/L during a follow-up unscheduled visit [normal range: 11 to 82 U/L]). None of the participants in either study required concomitant medications for the treatment of these TEAEs. There were no other clinical laboratory (hematology, biochemistry and urinalysis) results, vital signs measurements or routine 12-lead ECG measurements reported as TEAEs during the conduct of these studies. None of the participants had potentially clinically significant values or increases in liver enzymes or TBL after study intervention administration.

In the AME study 0367-CL-1103, 1 participant experienced a TEAE (diarrhea) that was considered by the investigator to be possibly related to study intervention. There were no clinical laboratory (hematology, biochemistry and urinalysis) results, vital sign measurements or routine 12-lead ECG measurements reported as TEAEs during the conduct of this study. No participant had potentially clinically significant increases in liver enzymes or TBL after study intervention administration.

ASP0367 has also been assessed in 1 completed phase 1b clinical study (0367-CL-0102) in late ambulatory and early non-ambulant patients with DMD. No SAEs, drug-related TEAEs, TEAEs leading to death or TEAEs leading to withdrawal of treatment were observed in the

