(PPARδ target gene expression)	missed assessments can be acceptable	
	where unfeasible.	
Neuro-QoL Short Form Fatigue,	Recommended to be performed onsite but	
Neuro-QoL Short Form Lower	missed assessments are acceptable when	
Extremity Function (Mobility),	the duration of the site visit should be	
MFIS, PGIC, and PGIS	minimized.	
Dispense/Collect IP	Direct-to-patient shipment is allowed.	
Previous and concomitant treatment	Home visits with follow-up phone call are	
	allowed.	
Exercise status	Home visits with follow-up phone call are	
	allowed.	
Adverse event assessment	Home visits with follow-up phone call are	
	allowed.	

STUDY INTERVENTION SUPPLY

If any of the conditions outlined above in the Participants Procedures Assessment are met, the following mitigating strategy will be employed, as needed, to ensure continuity of study intervention supply to the participants:

• Direct-to-Participant (DTP) shipments of study intervention from the site to the participant's home.

DATA COLLECTION REQUIREMENTS

Additional data may be collected in order to indicate how participation in the study may have been affected by a crisis and to accommodate data collection resulting from alternate measures implemented to manage the conduct of the study and participant safety.

• Critical assessments for safety and efficacy based on study endpoints to be identified as missing or altered (performed virtually, at alternative locations, out of window or other modifications) due to the crisis.

10.9	Appendix 9	List of Normal Ranges for Selected Laboratory
	Assessments	

Analyte	Sex	Age	Reference Range
Troponin T (cTnT)	Both	\geq 18 years	\leq 14.0 pg/mL
Troponin I (cTnI)	Both	≥ 0 years	\leq 0.06 ng/mL

Source: Laboratory Specifications Document v11 (06 Nov 2023)

Abbreviations	Description of abbreviations
5XSTS	5 Times Sit to Stand
6MWT	6-minute walk test
AE	adverse event
ALDOA	aldolase A
ALP	alkaline phosphatase
ALT	alanine aminotransferase
AME	absorption, metabolism and excretion
API	Astellas Pharma Inc.
AST	aspartate aminotransferase
AT	aminotransferases
AUC ₂₄	area under the concentration-time curve from the time of dosing to 24 hours
AUC _{inf}	area under the concentration-time curve from zero to infinity
AUC _{last}	area under the concentration-time curve from the time of dosing to the last measurable concentration
AV	atrioventricular
AVAPS	average volume-assured pressure support
BCRP	breast cancer resistance protein
BiPAP	bilevel positive airway pressure

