5.2.6 Laboratory test (hematology, biochemistry and urinalysis)

Safety laboratory tests will be done by a central laboratory from the screening to the end of the study. The scheduled visit and the list of clinical laboratory tests are described in the protocol.

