6.5.2.1 Liver Safety Assessment

The liver safety assessments will be summarized by the categories below based on the measurements from ALP, ALT, total bilirubin, AST and their combination. These parameters will be based on measurements from a local laboratory. If the baseline value is above ULN then use the baseline value instead of ULN.

- ALT > ULN, > 2xULN, > 3xULN, > 5xULN, > 10xULN, > 20xULN
- AST > ULN, > 2xULN, > 3xULN, > 5xULN, > 10xULN, > 20xULN
- ALT or AST > ULN, > 2xULN, > 3xULN, > 5xULN, > 10xULN, > 20xULN
- ALP > 1.5xULN, 2xULN, 2.5xULN
- Total Bilirubin > 2xULN
- (ALT or AST > 3xULN) and Total Bilirubin > 2xULN
- (ALT or AST > 3xULN) and ALP < 2xULN and Total Bilirubin > 2xULN

The last 2 criteria where 2 or more parameters are evaluated will be with the measurements on the same day or up to 1 day apart.

The denominator for each criterion will be the number of participants who have at least one value after the day of first ASP0367 taken to 28 days after the last dose of ASP0367. The number and percentage of participants meeting the criteria by 28 days after the last dose of ASP0367 will be summarized by analysis group.

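### The 76-week SAP flags laboratory results by site-supplied ranges, although safety samples are said to be run centrally; the range should be that of the laboratory that ran the sample

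*SAP*

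**What the plan says.** The SAP document holds two plans, one for the 52-week double-blind part and one for up to 76 weeks including the open-label extension. The point sits mainly in the second.

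- **76-week SAP, 6.5.2 (Clinical Laboratory Evaluation):** every laboratory result is put into a low, normal or high class at each visit "according to the site supplied reference ranges". The section also plans counts of amylase, lipase and troponin above ULN and above 2xULN, without naming whose ULN.
- **76-week SAP, 5.2.6 (Laboratory test):** "Safety laboratory tests will be done by a central laboratory from the screening to the end of the study". The 52-week SAP says the same in 5.4.6.
- **Protocol, Table 1, footnote g:** "Safety laboratory will be done by a central laboratory from the screening to EOS".
- **76-week SAP, 6.5.2.1 (Liver Safety Assessment),** on ALP, ALT, AST and total bilirubin: "These parameters will be based on measurements from a local laboratory". The 52-week SAP has the same sentence under the same number.
- **Protocol, Appendix 9 (10.9):** one study-wide range for each troponin, cTnI up to 0.06 ng/mL and cTnT up to 14.0 pg/mL. The source given is a laboratory specification document, version 11, dated 06 Nov 2023.

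The low/normal/high sentence has no counterpart in 6.5.2 of the 52-week SAP. Protocol 9.4.3.2 plans only descriptive statistics for quantitative laboratory measurements.

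**The concern.** A reference range belongs to the assay and laboratory that produced the value. If samples go to a central laboratory and the ranges come from the sites, two things can go wrong. A value can be flagged high or low when its own laboratory would call it normal, or the reverse. The same value can also be flagged differently at two sites.

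The protocol names cardiac and skeletal muscle toxicity as important potential risks (2.3.1.3), and troponin and CK limits define adverse events of special interest (AESIs). The only range source that 6.5.2 names is the sites, so a programmer could carry it into the ULN and 2xULN tables and into the AESI criteria in 6.5.1, neither of which states a source.

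**Working it through.** There is no figure in the plan to reproduce. The check is a comparison of statements, followed by a hand illustration.

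**Step 1. Which laboratory, and whose range?**

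| Place | Data covered | Laboratory | Source of range or ULN |
|---|---|---|---|
| Protocol, Table 1, footnote g | safety laboratory | central | not stated |
| 76-week SAP 5.2.6; 52-week SAP 5.4.6 | safety laboratory tests | central | not stated |
| 76-week SAP 6.5.2, low/normal/high | each laboratory result | not stated | sites |
| 76-week SAP 6.5.2, ULN and 2xULN | amylase, lipase, troponin | not stated | not stated |
| 76-week SAP 6.5.1, AESI criteria | cTnI, cTnT, CK | not stated | not stated |
| Both SAPs, 6.5.2.1 | ALP, ALT, AST, total bilirubin | local | not stated |
| Protocol, Appendix 9 | cTnI, cTnT | one laboratory specification | study-wide limits |

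Two conflicts follow. Central results are paired with site ranges. The liver tests, which are part of the biochemistry panel in protocol Appendix 6, are central by footnote g but local by 6.5.2.1.

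**Step 2. Can the choice of range change a class?** The protocol happens to quote three cTnI upper limits: 0.015 ng/mL in the renal impairment study ("normal range: not reported to 0.015 ng/mL"), 0.045 ng/mL in the first-in-human study, and 0.06 ng/mL in Appendix 9. The spread is 0.06 / 0.015 = 4-fold. One first-in-human participant had readings of 0.056 and then "0.047 ng/mL above the ULN of 0.045 ng/mL". The renal study reported a value of 0.09 ng/mL.

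| cTnI (ng/mL) | ULN 0.015 | ULN 0.045 | ULN 0.06 |
|---|---|---|---|
| 0.047 | high | high | normal |
| 0.056 | high | high | normal |
| 0.09 | high | high | high |
| 0.09 against 2xULN (0.03; 0.09; 0.12) | above | equal, not above | not above |

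So a range from the wrong laboratory can move a value across the ULN or the 2xULN line. This shows the mechanism only. The first two limits come from other studies and are not site ranges in this trial.

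**Step 3. Which outputs could be affected?**

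- Means, standard deviations and changes from baseline use no range, so they are unaffected.
- The SAP describes no shift table or count by low/normal/high class. Table formats are left to a separate specification that is not among the documents.
- The ULN and 2xULN counts and the AESI criteria are affected only if the site ranges are carried over to them, which the text neither says nor excludes.
- The 76-week analysis compares participants assigned to ASP0367 with participants who switched from placebo to ASP0367. It has no concurrent placebo group.

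**The case against.** The strongest reply has four parts.

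1. **Site-supplied may be loose wording** for the range that arrives with each result. That is possible, and the practical effect would then be nil. The sentence would still contradict 5.2.6.
2. **Not every analysed value need be central.** A reader might infer from 5.2.6 and footnote g that all safety values are central, so that every site-based flag is wrong. The documents do not support that, because 6.5.2.1 in both SAPs takes the four liver tests from a local laboratory. For a value truly measured locally, the local range is the right one. This limits the point, but it also shows that the plans disagree on which laboratory's data are analysed.
3. **The consequences are modest.** A reader might infer that shifts to high in troponin, CK, amylase and lipase, the trial's main safety signals, are at risk. No such shift analysis is described, and CK is not in the ULN summary. A reader might also expect a clash between the flags and an AESI rule tied to Appendix 9. The SAP's AESI definition does not cite that appendix (protocol 7.3.6 does) and also requires a matching treatment-emergent adverse event, so flags and AESI counts could differ even with identical ranges.
4. **Imposing the Appendix 9 limits on all troponin results is not clearly right.** Their source is dated 06 Nov 2023, whereas the SAP says that all participants took part under protocol version 7.0 or earlier. The documents do not show that those limits applied when earlier samples were run.

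Parts 2 to 4 stand and set the limits of the point. Part 1 cannot be settled from the documents and does not remove the contradiction.

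**Conclusion.** The classification rule in 6.5.2 of the 76-week SAP is wrong as written. Followed literally, it flags central results against ranges from other laboratories, and the liver subsections leave it unclear which laboratory's results are analysed at all.

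The effect is confined to low/normal/high flags, and possibly to ULN-based counts, in the 76-week descriptive safety analysis. The sentence is absent from the 52-week SAP, so it does not reach the placebo-controlled laboratory summaries. The liver-laboratory conflict does appear in both plans.

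No size can be given. The documents contain no site range for this trial and no patient-level values. The 4-fold spread in quoted cTnI limits should not be read as a misclassification rate. The conclusion assumes that the sentence means what it says and that safety samples were in fact run centrally, as 5.2.6 and footnote g state.

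**What to change.** Four edits to the SAP text:

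1. Reconcile 5.2.6, 6.5.2 and 6.5.2.1 of the 76-week SAP, and 6.5.2.1 of the 52-week SAP, with footnote g of protocol Table 1. State which laboratory's results are analysed for each group of tests.
2. In 6.5.2 of the 76-week SAP, replace the site-supplied ranges with the reference range of the laboratory that ran the sample. For central results this is the central range in force at the time; a local range applies only to values measured locally.
3. State that the ULN and 2xULN summaries of amylase, lipase and troponin, and the AESI criteria, use the same source.
4. Name the output that uses the low/normal/high classes, or delete the sentence if there is none.

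The cost is a few lines of text. No new data should be needed if the ranges are transferred with the laboratory results, which the study team should confirm. If tables have already been programmed with site ranges, the flags and any dependent counts would have to be rerun.
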